#### 9. RESEARCH METHODS

#### 9.1. Study Design

All assessments described in this protocol are performed as part of normal clinical practice or standard practice guidelines for the patient population and HCP specialty in the countries where this NIS is being conducted.

The following study will be managed by Adelphi Real World, acting as the Clinical Research Organisation (CRO) in collaboration with Pfizer. The protocol and study methods will be reviewed by principal investigators in the UK, US and Spain to ensure scientific and clinical merit. The study will be an international site-led (approximately 13 sites) retrospective observational chart review, assessing the characteristics and clinical outcomes of R/R ALL patients who received InO as a bridging therapy to CAR-T. Sites will be based in the US, UK, and Spain. Sites will be responsible for identifying eligible patients, electronic data abstraction and data query resolution. Clinicians and site staff will abstract data from adult R/R ALL eligible patients' medical records, with index defined as those initiating InO treatment as a bridge to CAR-T from index date 01 June 2017, and enter the required datapoints within an electronic data capture (EDC) system. Baseline patient demographics and clinical and molecular characteristics will be evaluated at index. Treatment patterns and effectiveness outcomes will be described throughout the follow-up period. Patients included will be required to have a minimum follow-up of 3 months defined as patients with 3 months of data following the first dose of InO to database extraction (patients who have died within 3-months of InO administration would be considered eligible for inclusion). See Figure 1 for the study schematic.

#### Figure 1. Study Schematic, eCRF Design

#### \*Permitted exceptions to the minimum 3-month follow-up requirement include:

- Patients who die within the 3 months
- Patients who proceed to a CD19 CAR-T clinical trial within the 3 months

The study aims to assess the demographics and clinical and molecular characteristics of patients, as a primary objective. The study also aims to describe treatment effectiveness and treatment patterns as secondary objectives. See Section 8 and Section 9.3 for a breakdown of the specific endpoints and variables of interest. Details of the study period are shown in Figure 1.

### 9.2. Setting

R/R ALL patients aged 18 years and above initiating InO treatment as a bridge to CD19-directed CAR-T from index date 01 June 2017 (first InO approval) will be identified within the sites based in UK, US and Spain, using the inclusion and exclusion criteria specified below. The indexing period should allow for a large proportion of patients treated with InO prior to CAR-T at these sites to be gathered, following US Food and Drug Administration (FDA) and EMA approval of InO in 2017, and CAR-T approval from 2017. No formal sampling will be conducted in any country. Sites selected for chart review methodology will complete data collection for all eligible patients.

Potential sites participating in the retrospective chart review will be invited to complete a short feasibility questionnaire prior to site selection. The feasibility questionnaire will be used to confirm suitability of sites for inclusion, confirming study critical information such as InO patient caseload and data availability. Additionally, logistical information pertaining to site contracting and IRB processes will also be assessed. A number of sites across the three countries have already been assessed to provisionally confirm feasibility. Following completion of the feasibility phase of the study and the subsequent set-up activities for selected sites, eCRFs will be completed by clinicians and site staff at the sites for patients meeting the inclusion/exclusion criteria below.

#### 9.2.1. Inclusion Criteria

Patients must meet all of the following inclusion criteria to be eligible for inclusion in the study:

1. Patient has a clinical diagnosis of R/R PBC ALL

PFIZER CONFIDENTIAL

Redacted

- 2. Patient is aged 18 years or older at start of InO therapy
- 3. Patient received InO treatment as a bridge to CD19-directed CAR-T cell therapy (is defined as either patient received InO immediately prior to apheresis, and/or patient received InO after apheresis and before CAR-T cell infusion. In either case, InO was used with the aim of preventing uncontrolled disease progression and facilitating successful progression to CAR-T cell therapy. Such patients are eligible to be included even if CAR-T was not ultimately administered from index date (01 June 2017)
- 4. Patients with data points available for a minimum of 3 months data from the first dose of InO are eligible for inclusion within the study. Permitted exceptions to the minimum 3-month follow-up requirement include:
  - a. Patients who die within the 3 months
  - b. Patients who proceed to a CD19 CAR-T clinical trial within the 3 months

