#### Screener:

Variable	Role	Data source(s)	Operational definition	Time-point
Has this patient been diagnosed with R/R B-cell leukaemia ALL?	To determine eligibility for study	eCRF	R/R (PBC) ALL diagnosis	R/R (PBC) ALL diagnosis
Patient's age (or one categorical response if aged $\ge 90$ )	To determine eligibility for study	eCRF	Patients age at InO 1 st dose	1 st dose of InO (index)
Did the patient initiate InO treatment 01 June 2017 onwards as a bridging therapy to intended CAR-T?	To determine eligibility for study	eCRF	InO initiation as bridge to CAR-T date	1 st dose of InO (index)
Is the patient currently alive?	To determine eligibility for study	eCRF	Patient's vital status	Anytime up to/including data collection

Variable	Role	Data source(s)	Operational definition	Time-point
Does the patient have at least 3 months' follow up data from the first dose of InO to the date of last assessment? Note: Patients who die within the 3 months or proceed to a CD19 CART clinical trial are eligible for inclusion within the study	To determine eligibility for study	eCRF	Follow up status	1 st dose of InO (index) to date of last assessment
Has the patient received at least one dose of InO bridging to CAR-T therapy and then completed CAR- T therapy (if they could receive it)?	To determine eligibility for study	eCRF	InO bridging therapy status	Anytime up to/including data collection

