#### 9.7. Data Analysis

The study is not intended to test hypotheses and is primarily descriptive in nature, therefore descriptive analysis will be conducted to meet the majority of the pre-specified objectives. Frequencies and percentages will be reported for categorical variables, including the percentage of missing/unknown data, while counts, number of missing, means, medians, standard deviations (SDs), first and third quartiles, minimum and maximum values will be reported for continuous numeric variables. Where applicable, all estimates will be described with accompanying 95% confidence intervals (CI). Outcomes such as OS will be assessed via time to event analyses, with KM curves and 95% CI estimated for KM curves outputted. This will be calculated using variables in the CRF. For example, OS will be calculated from the first dose of InO to point of death. Censoring will be applied if the patient is alive at the point of data capture.

Data analysis will be aligned with data extracted/collected from all data sets. Where specific variables or outcomes cannot be assessed/described subgroup analyses could be conducted for a subset of patients from certain data sources.

All analyses will be conducted using Stata 17 software, version 17 or the latest available version (StataCorp, College Station, Texas).

Detailed methodology for summary and statistical analyses of data collected in this study will be documented in a statistical analysis plan (SAP), which will be dated, filed, and maintained

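### The 3-month follow-up criterion keeps early deaths but excludes most survivors with short charts, which can only lower early overall survival; the end of the 3-month window is also stated two ways

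*Protocol*

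**What the plan says.** Criterion 4 in Protocol 9.2.1, repeated in the Abstract under Population, reads "Patients with data points available for a minimum of 3 months data from the first dose of InO are eligible for inclusion within the study". Two exceptions follow: "Patients who die within the 3 months" and "Patients who proceed to a CD19 CAR-T clinical trial within the 3 months".

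The end of the 3-month window is given in two ways:

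- Section 9.1 requires a "minimum follow-up of 3 months defined as patients with 3 months of data following the first dose of InO to database extraction", and adds that "patients who have died within 3-months of InO administration would be considered eligible for inclusion". The Figure 1 footnote, still within 9.1, lists both exceptions.
- The screener in Section 9.3 asks for 3 months of "follow up data from the first dose of InO to the date of last assessment", and its note names both exceptions. The Abstract's list of variables also runs the window to last assessment.

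On survival, Section 9.7 states that "OS will be calculated from the first dose of InO to point of death", with patients alive at data capture censored. Section 9.9 says the 3-month minimum may leave OS and event-free survival unassessable for many patients, who will be censored. It gives no reason for the minimum and does not mention that the minimum selects patients.

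**The concern.** Eligibility is decided by what happens after the survival clock has started, and not symmetrically. A patient who dies in month 2 is in. A patient last seen alive in month 2 is out, unless that patient entered a CD19 CAR-T trial. One of the two exceptions is the OS event itself. Early deaths are therefore all counted while part of the risk set they belong to is removed.

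Two things are at stake. First, early survival is described as slightly worse than it is, in a study designated a post-authorisation safety study. Second, patients who could contribute to the primary objective are discarded, although that objective is demographics and clinical characteristics, recorded largely at index or at diagnosis.

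The two end points may also admit different patients. Measured to database extraction, the rule can be read as dropping mainly recent starters. Measured to last assessment, it drops anyone lost within 3 months in any year since 2017.

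**Working it through.** **Inputs from the protocol.** Minimum of 3 months from first inotuzumab ozogamicin (InO) dose, with the death and trial exceptions (9.2.1). OS from the same dose, Kaplan-Meier with censoring (9.7). Index window from 01 June 2017 (9.2). Data collection 16 December 2024 to 16 June 2025 (Section 6). Expected n = 79, a feasibility count with no alpha, power or effect size behind it (9.5), so there is no calculation of the plan's own to reproduce.

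**Assumptions.** The protocol gives neither early mortality nor the share of short charts. I take exponential survival with true 3-month survival s from 90% to 60%. A share q of patients has a chart that closes at a time uniform over 0 to 3 months, independently of death. The trial exception is left out of the model, so q refers to patients not rescued by it.

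**Direction.** Each Kaplan-Meier factor is 1 − (deaths)/(number at risk). Removing patients censored alive before month 3 reduces the number at risk at earlier deaths and removes no death. Every factor falls or stays the same, so the curve cannot rise.

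**Size.** Let m be the mean probability of being alive when a short chart closes:

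- m = (1 − s)/(−ln s)
- survivors to month 3 retained: a = (1 − q)s
- deaths observed before month 3: d = (1 − q)(1 − s) + q(1 − m)
- excluded: qm
- 3-month OS under the rule: a/(a + d)

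Example with s = 0.80 and q = 0.10: m = 0.20/0.2231 = 0.896; a = 0.720; d = 0.180 + 0.0104 = 0.1904; OS = 0.720/0.9104 = 0.791. This is 0.91 points too low, and 9.0% of otherwise eligible patients are excluded.

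**Choice of q.** From 01 June 2017 to 16 December 2024 is 90.5 months, and to 16 June 2025 is 96.5 months. Under even accrual the last 3 months hold 3/90.5 = 3.3% or 3/96.5 = 3.1% of patients. If accrual fell within the last 36 months, 3/36 = 8.3%. Values of 10% and 20% stand for loss to follow-up under the last-assessment reading.

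Change in 3-month OS, in percentage points:

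| q | s = 90% | s = 80% | s = 70% | s = 60% |
|---|---|---|---|---|
| 3.1% | −0.15 | −0.26 | −0.35 | −0.41 |
| 8.3% | −0.41 | −0.74 | −0.99 | −1.16 |
| 10% | −0.51 | −0.91 | −1.21 | −1.41 |
| 20% | −1.13 | −2.02 | −2.67 | −3.09 |

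**Simulation check.** 4000 datasets of 79 patients per scenario, true 3-month OS 80%:

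| q | All patients, censored | Criterion 4 | Selected on potential follow-up, any vital status |
|---|---|---|---|
| 3.1% | 80.0% | 79.7% | 80.0% |
| 10% | 79.9% | 79.0% | 79.9% |
| 20% | 80.1% | 78.0% | 80.0% |

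At q = 20%, mean 12-month OS was 41.1% with censoring and 40.0% under criterion 4.

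**Scale.** The 95% half-width at n = 79 and OS 80% is 1.96 × √(0.8 × 0.2/79) = 8.8 points.

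**The case against.** The strongest reply is that this hardly matters. Survival is a secondary, descriptive outcome. The only value of q tied to dates in the protocol is about 3%, which costs under half a point, and even 3 points lies well inside the confidence interval. That stands, and it limits the point to a small error.

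A downward shift is a bias only if censoring is independent. If patients who leave early die sooner than those followed, ordinary censoring overstates survival, and excluding them partly offsets this. That also stands as a condition on the size.

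A minimum window may make response and next-treatment data more complete, so it would be too strong to say the rule brings no gain. The protocol does not make this argument, however. Section 9.9 retains patients in Spain who have no data from CAR-T infusion onwards, because the primary objective is unaffected; the same reasoning covers a survivor with a 2-month chart.

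Four stronger readings are tempting but unsupported:

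- A reader might infer that Section 9.1 omits the trial exception. Its running text names only death, but the Figure 1 footnote in the same section lists both.
- A reader might take 9.1 as the unbiased version because it runs to database extraction. It still keeps early deaths while dropping survivors, so it shares the asymmetry; its wording can also be read as data available rather than time elapsed.
- A reader might subtract the excluded patients from 79. Section 9.5 introduces that figure while speaking of patients who meet the criteria, so it reads as the number expected after criterion 4.
- A reader might suppose that patients treated with commercial CAR-T elsewhere are dropped as a class. They are excluded only if their chart holds under 3 months of data.

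**Conclusion.** The asymmetry is in the text, and its direction follows from arithmetic: criterion 4 can only lower the early Kaplan-Meier estimate. Under independent censoring and exponential survival, the fall at 3 months is about 0.15 to 0.4 points if only recent starters are dropped with even accrual. It is 0.5 to 1.4 points if 10% of charts are short and 1.1 to 3.1 points if 20% are. Those two shares are assumptions. The number of patients lost to the primary description is unknown.

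The selection is not disclosed in 9.9, although items 7.2 and 12.1.1 of the ENCePP checklist point there for selection bias. The two end points of the window need reconciling whatever one thinks of the bias. The case for changing the rule rests on a one-directional and avoidable selection, some loss of scarce patients and a cheap remedy. It does not rest on a large error in OS.

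**What to change.** Make eligibility independent of vital status and of actual follow-up, by one of two routes:

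1. Remove the 3-month minimum and its exceptions.
2. Require only that the first bridging InO dose was given at least 3 months before a defined data extraction date, whatever the later course, and delete both exceptions.

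Under either route, include all such patients and censor those alive at last contact. Section 9.3 already collects the last date of activity for patients lost to follow-up. State the same rule in the Abstract (Population and Variables), the text of 9.1, the Figure 1 footnote, criterion 4 in 9.2.1 and the screener item.

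The cost is one criterion and one screener item reworded, with the matching text aligned, and a few more charts to abstract. Some of these will have short follow-up and less complete response data. Under the second route, recent starters who died, whom the protocol now keeps, would no longer be included. This version is dated 09 May 2025 and collection is planned to end on 16 June 2025, so sites may need to look again at patients already screened out on this item.

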#### 9.2.2. Exclusion Criteria

There are no exclusion criteria for this study.

#### 9.3. Variables

The CRF captures all data variables of interest therefore allowing research objectives to be addressed. Final variables will be confirmed upon finalisation of the CRF.

#### Screener:

Variable	Role	Data source(s)	Operational definition	Time-point
Has this patient been diagnosed with R/R B-cell leukaemia ALL?	To determine eligibility for study	eCRF	R/R (PBC) ALL diagnosis	R/R (PBC) ALL diagnosis
Patient's age (or one categorical response if aged $\ge 90$ )	To determine eligibility for study	eCRF	Patients age at InO 1 st dose	1 st dose of InO (index)
Did the patient initiate InO treatment 01 June 2017 onwards as a bridging therapy to intended CAR-T?	To determine eligibility for study	eCRF	InO initiation as bridge to CAR-T date	1 st dose of InO (index)
Is the patient currently alive?	To determine eligibility for study	eCRF	Patient's vital status	Anytime up to/including data collection

Variable	Role	Data source(s)	Operational definition	Time-point
Does the patient have at least 3 months' follow up data from the first dose of InO to the date of last assessment? Note: Patients who die within the 3 months or proceed to a CD19 CART clinical trial are eligible for inclusion within the study	To determine eligibility for study	eCRF	Follow up status	1 st dose of InO (index) to date of last assessment
Has the patient received at least one dose of InO bridging to CAR-T therapy and then completed CAR- T therapy (if they could receive it)?	To determine eligibility for study	eCRF	InO bridging therapy status	Anytime up to/including data collection

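### The eligibility wording is inconsistent on whether a patient must reach apheresis or CAR-T, and may leave some early failures out of an OS clock that starts at the first InO dose

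*Protocol*

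**What the plan says.** Section 9.2.1 requires all inclusion criteria to be met. Criterion 3 defines InO as a bridge through two routes: "patient received InO immediately prior to apheresis, and/or patient received InO after apheresis and before CAR-T cell infusion". It then states the aim of such use (disease control on the way to CAR-T) and adds: "Such patients are eligible to be included even if CAR-T was not ultimately administered". The abstract repeats this.

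Criterion 4 sets the follow-up minimum: "Patients with data points available for a minimum of 3 months data from the first dose of InO are eligible". Patients who die within the 3 months, or who enter a CD19 CAR-T trial within them, are exempt from it.

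The screener table in section 9.3 has two items that bear on the same question, both given an eligibility role. One asks about intent at index: did the patient "initiate InO treatment 01 June 2017 onwards as a bridging therapy to intended CAR-T". The other asks about a later event, assessed at any time up to data collection: has the patient "received at least one dose of InO bridging to CAR-T therapy and then completed CAR- T therapy (if they could receive it".

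Section 9.7 fixes the time origin: "OS will be calculated from the first dose of InO to point of death". Patients alive at data capture are censored. Section 9.9 discusses selection bias from site participation and consent, but not from entry rules that depend on events after the first dose.

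**The concern.** Entry to the cohort should be settled by what is known at the first InO dose, because that is where the survival clock starts. Two pieces of wording can make it depend on what happened afterwards.

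First, the completion item asks about CAR-T completion inside an eligibility table. Its bracketed qualifier does not say who counts as unable to receive CAR-T. A patient who progressed or died on InO can be read as unable to receive it, and kept, or as not having completed it, and screened out. Staff at about 13 sites in three countries decide this chart by chart.

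Second, the allowance for patients never given CAR-T refers back to patients who already fit one of the two routes. It speaks of administration of CAR-T, not of failure to reach apheresis. The exemption for deaths within 3 months waives criterion 4 only.

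If patients are lost this way, the time from first InO dose to the milestone becomes guaranteed survival time for those who must reach it. Survival is a stated secondary objective. The study is also a designated PASS that collects veno-occlusive disease and cause of death, and fatal events before apheresis are the records most exposed to loss.

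**Working it through.** **Step 1: the passages side by side.** Four kinds of patient, all given InO with CAR-T in view:

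| Patient | Criterion 3 | Completion item in the screener |
|---|---|---|
| InO, apheresis, infusion (either order of InO and apheresis) | Eligible | Yes |
| InO after apheresis, failed before infusion | Eligible by the non-administration allowance | Depends on how the bracket is read |
| InO before apheresis, apheresis done, failed before infusion | Eligible by the same allowance | Depends on how the bracket is read |
| InO before a planned apheresis, died or progressed before it | Fits neither route literally; the aim sentence and the item on intended CAR-T point to inclusion | Depends on how the bracket is read |

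So there are two defects: a conflict between criterion 3 and the completion item (rows 2 and 3), and a gap in criterion 3 itself (row 4).

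**Step 2: inputs for the size.** From the protocol: n = 79, a feasibility count (section 9.5), and OS from the first InO dose (section 9.7). It states no OS rate, median, apheresis timing or share starting InO before apheresis, so there is no figure to reproduce. Assumptions: exponential survival with median m = 6, 8 or 12 months; apheresis t0 = 0.5 to 3 months after the first dose; a share f = 25 to 50% starting InO before apheresis.

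**Step 3: apheresis condition only.** With S(t) = 2^(−t/m), only the share f can be lost, so

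observed 12-month OS = S(12) / [f·S(t0) + (1 − f)].

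- Low end, m = 6, t0 = 0.5, f = 0.25: S(12) = 0.2500, S(0.5) = 0.9439, denominator 0.25 × 0.9439 + 0.75 = 0.9860, result 0.2536, a rise of 0.4 points.
- Middle, m = 8, t0 = 2: S(12) = 0.3536, S(2) = 0.8409. With f = 0.25: 0.3536 / 0.9602 = 0.368 (+1.5 points). With f = 0.50: 0.3536 / 0.9204 = 0.384 (+3.1 points).
- High end, m = 8, t0 = 3, f = 0.50: S(3) = 0.7711, denominator 0.8856, result 0.3992, a rise of 4.6 points.

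The share of InO starters lost is f·[1 − S(t0)]. It runs from 0.25 × (1 − 0.9715) = 0.7% (m = 12, t0 = 0.5) to 0.50 × (1 − 0.7071) = 14.6% (m = 6, t0 = 3).

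**Step 4: completion item used as a gate.** Every patient must then survive to the milestone, so observed 12-month OS = S(12)/S(t0). Over the same medians and with the milestone 0.5 to 3 months after the first dose, the rise runs from 0.5000 / 0.9715 = 0.515 (+1.5 points; m = 12, t0 = 0.5) to 0.3536 / 0.7711 = 0.459 (+10.5 points; m = 8, t0 = 3).

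**Step 5: inclusion by intent.** No one is lost, and 12-month OS equals S(12). The rise is zero.

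**Step 6: scale.** Ignoring censoring, the 95% half-width at n = 79 is 1.96 × √(0.3 × 0.7/79) = 0.101 at 30% and 1.96 × √(0.5 × 0.5/79) = 0.110 at 50%, so about 10 to 11 points.

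These figures count deaths before the milestone only. Patients dropped alive after progression would add to the rise if their later survival is poor; that part is not sized here.

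**The case against.** Much of the text points to including early failures. Criterion 3 expressly admits patients never given CAR-T and describes the aim of treatment. Another screener item speaks of intended CAR-T. Deaths within 3 months are exempt from the follow-up minimum. The bracket in the completion item can cover most patients who fail before infusion. Nor does the eligibility label prove that a yes is required: the item asking whether the patient is alive carries the same label, and deceased patients are plainly eligible. The protocol says variables are final only when the CRF is final. OS is one of several secondary descriptive outcomes, and a SAP could specify delayed entry.

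Most of this stands, and it rules out two stronger readings. A reader might infer that early failures do drop out and that reported survival is inflated; the documents show only that they may, depending on how sites read the wording. A reader might also size the bias by comparing all patients with CAR-T completers. With an assumed 20% non-completers at median 3 months and the rest at 15 months, 12-month OS is 0.8 × 0.574 + 0.2 × 0.0625 = 0.472 against 0.574, a 10-point gap. That models a completers-only cohort, which criterion 3 rejects, on shares and medians found nowhere in the documents.

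Nor is it right that the plan hides failure to reach CAR-T. For enrolled patients the eCRF records the next step after InO, leukapheresis dates and success, and the infusion date.

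What the objection does not answer is the conflict itself, the patient who fits neither route, and the fact that no SAP can recover patients who were never entered in the eCRF.

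**Conclusion.** The concern holds as an internal inconsistency that may exclude some early failures. The completion item conflicts with criterion 3, and criterion 3 does not literally cover a patient who started InO before a planned apheresis and failed first. Any resulting bias in OS is upward, given that the patients lost are those who die or do worse.

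For the apheresis condition, the bias can arise only among patients who start InO before apheresis; those who start after it carry no guaranteed survival time from that condition. Under the assumptions in the working, it is roughly 0.4 to 4.6 points at 12 months, and zero if sites apply intent. It is larger, about 1.5 to 10.5 points over the same range of medians and milestone times, only if sites use the completion item as a gate. The upper end of that is about the width of the 95% interval's half-width at n = 79, and the reported intervals would not reveal it. Whether any bias occurs, and how much, cannot be determined from the protocol.

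**What to change.** - Remove CAR-T completion from the eligibility screener and keep it as a recorded outcome.
- Reword criterion 3 so that it covers InO started with charted intent to proceed to CD19 CAR-T, whether or not apheresis or infusion followed. Make the same change in the abstract.
- Ask sites to re-check patients already screened out, and complete this before database lock.
- Report the flow from InO start to apheresis to infusion, using variables the eCRF already collects.
- If patients can be found only through apheresis records, analyse OS with delayed entry at apheresis for those who started InO before it.

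The cost is a wording amendment and a re-screen at about 13 sites, against a planned end of data collection of 16 June 2025. The small downside is that intent has to be judged from the chart for patients who never reached apheresis.
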